6.9. Treatment after the End of the Study

Subjects will not receive any additional treatment from GSK after completion of the study because only healthy adult subjects are eligible for study participation.

6.10. Lifestyle and/or Dietary Restrictions

6.10.1. Meals and Dietary Restrictions

Standardized meals will be provided while the subject is confined to the clinical unit. At all mealtimes, food will be served only after completion of protocol-specified procedures.

Subjects will refrain from consumption of red wine, Seville oranges, grapefruit, or grapefruit juice (and/or pummelos, exotic citrus fruits, grapefruit hybrids, or fruit juices) from 7 days before the first dose of study drug until after the final dose.

Water will be allowed ad libitum except for 1 hour before the start of infusion and 1 hour after the end of infusion.

Subjects will fast from food and drink (except water) for at least 10 hours before dosing on Day 1 (Parts 1, 2, and 3) and Day 15 (Part 2 only). Meals at all other times will be provided at times that will not interfere with fasting required for clinical laboratory testing.

These fasting requirements may be removed or modified at the discretion of the sponsor in consultation with the investigator.

6.10.2. Caffeine, Alcohol, and Tobacco

Subjects will abstain from ingesting caffeine- or xanthine-containing products (e.g., coffee, tea, cola drinks and chocolate) for 24 hours before the start of dosing on Day 1 until collection of the final PK sample.

Subjects will abstain from alcohol for 24 hours before the start of dosing on Day 1 until collection of the final PK sample.

Use of tobacco products is not allowed from 3 months before screening until after the final Follow-up visit.

6.10.3. Activity

Subjects will abstain from strenuous exercise during the course of the study through the Follow-up visit. Subjects may participate in light recreational activities during the study (e.g., watch television, read).

6.11. Concomitant Medications and Non-Drug Therapies

6.11.1. Permitted Medications and Non-Drug Therapies

Paracetamol or Acetaminophen at doses of ≤ 2 grams/day and HRT are permitted for use during the study. Other concomitant medication may be considered on a case-by-case basis by the investigator in consultation with the medical monitor.

6.11.2. Prohibited Medications and Non-Drug Therapies

Subjects must refrain from the use of prescription or non-prescription drugs, including vitamins and herbal and dietary supplements (including St John's Wort) within 7 days (or 14 days if the drug is a potential enzyme inducer) or 5 half-lives (whichever is longer) before the first dose of study drug, unless in the opinion of the investigator and GSK medical monitor, the medication will not interfere with the study procedures or compromise subject safety.

7. STUDY ASSESSMENTS AND PROCEDURES

Protocol waivers or exemptions are not allowed with the exception of immediate safety concerns. Therefore, adherence to the study design requirements, including those specified in the Time and Events Tables (Section 7.1) are essential and required for study conduct.

This section lists the procedures and parameters of each planned study assessment. The exact timing of each assessment is listed in the Time and Events Tables (Section 7.1).

The following points must be noted:

- If assessments are scheduled for the same nominal time, THEN the assessments should occur in the following order:
 1. 12-lead ECG
 2. vital signs
 3. blood draws

- Note: The timing of the assessments should allow the blood draw to occur at the exact nominal time.
 - The timing and number of planned study assessments, including safety and PK assessments may be altered during the course of the study based on newly available data (e.g., to obtain data closer to the time of peak plasma concentrations) to ensure appropriate monitoring.
 - The change in timing or addition of time points for any planned study assessments must be documented in a Note to File, which is approved by the relevant GSK study team member and then archived in the study sponsor and site study files; but, this will not constitute a protocol amendment.
 - The Institutional Review Board (IRB)/Independent Ethics Committee (IEC) will be informed of any safety issues that require alteration of the safety monitoring scheme or amendment of the informed consent form.
 - No more than 500 mL of blood will be collected over the duration of the study, including any extra assessments that may be required.

7.1. Time and Events Tables

Table 3 Time and Events Table: Screening and Day –1; Single and Repeat Dose Escalation (Part 1 and Part 2) and Single Dose (Part 3)

Procedure	Screening (up to 30 days before Day 1)	Day –1	Notes
Informed consent	X		
Inclusion and exclusion criteria	X	X	
Demography	X		
Medical history (includes substance usage and family history of premature cardiovascular disease)	X	X	Substances: drugs, alcohol, tobacco and caffeine.
Past and current medical conditions including cardiovascular medical history	X	X	
Safety and Laboratory Assessments			
SAE review	X	X	Serious AEs will be collected from the signing of informed consent.
Concomitant medication review	X	X	
Full physical examination including height and weight	X		
Brief physical examination		X	
Vital signs (BP, HR, oral temperature, respiration rate)	X	X	
12-lead electrocardiogram	X	X	
Continuous cardiac monitoring		X	Continuous dual-lead telemetry will be initiated on Day –1 at least 8 hours before study drug administration on Day 1.
Urine cotinine and drug and breath alcohol screens	X	X	
β-hCG pregnancy test/estradiol/FSH	X	X	Pregnancy test (if female of child-bearing age; serum at screening and urine at Day –1); estradiol and FSH at screening as appropriate. Only women of non-child-bearing potential may participate.
Human immunodeficiency virus antibody, hepatitis B surface antigen, and hepatitis C antibody screen	X		
Clinical chemistry (including liver chemistries), hematology, and urinalysis	X	X	The albumin to creatinine ratio will be determined at Screening using the first morning void urine as described in Section 7.3.7. An aliquot of the urine sample will be collected for NGAL and KIM-1 at Day –1. These samples may be analyzed after the end of the study if a clinical signal is detected. Instructions for collection and storage of these urine samples are included in the Study Reference Manual. Hematology assessments on Day –1 will also include total iron, total binding iron capacity, ferritin, haptoglobin, ceruloplasmin and reticulocytes.

Procedure	Screening (up to 30 days before Day 1)	Day -1	Notes
Table is continued on the next page.			
Blood collection for additional iron tests		X	In Part 2 only. Samples will be collected for potential analysis of some or all of the additional iron tests at the end of the study if a clinical signal is detected.
Genetic sample		X	Collect a pharmacogenomics sample only if the subject has a signed consent specific for this purpose. The pharmacogenomics sample can be collected anytime, but Day -1 is recommended. Informed consent for optional sub-studies (e.g., genetics research) must be obtained before collecting a sample.
Admission to clinical unit		X	
β -hCG = beta human chorionic gonadotropin, BP = blood pressure, FSH = follicle-stimulating hormone, HR = heart rate, KIM-1 = kidney injury molecule 1, NGAL = neutrophil gelatinase-associated lipocalin, SAE = serious adverse event.			

Table 4 Time and Events Table: Part 1 - Single Dose Escalation and Part 3 - Single Dose

Procedure	Day 1																	Day 2	Day 3	
	Hours relative to treatment administration																			
	Pre-dose	0	0.5	1	1.25	1.5	2	3	3.5	4	4.5	5	6	8	10	12	16	24	36	48
Randomization	X																			
12-lead ECG ¹	X		X	X		X	X	X		X			X			X		X		X
Vital signs (BP, HR, oral temperature, respiration rate)	X		X	X		X	X	X		X			X			X		X		X
Fasting clinical chemistry, hematology, and urinalysis ²																		X		
Treatment administration ³		X																		
Blood collection for pharmacokinetics ⁴	X		X	X	X	X	X	X	X	X	X	X	X	X	X	X	X	X	X	X
Urine collection for pharmacokinetics ⁵	X	X								X				X		X		X		X
Continuous cardiac monitoring ⁶	X	-----Continuous review----->																		
AE review		X	-----Continuous review----->																	
SAE review	X	-----Continuous review----->																		
Concomitant medication review	X	-----Continuous review----->																		
Discharge from inpatient unit ⁷																				X

AE = adverse event, BP = blood pressure, ECG = electrocardiogram, HR = heart rate, SAE = serious adverse event.

NOTES:

1. Triplicate 12-lead ECGs to be obtained at least 5 minutes apart within 1 hour before dosing. Single ECGs will be obtained at all other time points.
2. An aliquot of the urine sample will be collected for neutrophil gelatinase-associated lipocalin (NGAL) and kidney injury molecule 1 (KIM-1). These samples may be analyzed after the end of the study if a clinical signal is detected. Instructions for collection and storage of these urine samples are included in the Study Reference Manual. The albumin to creatinine ratio will be determined using the first morning void urine on Day 2.
3. GSK3342830 or placebo will be administered as a single IV infusion in the morning on Day 1. The planned infusion duration time is 1 hour.
4. Pharmacokinetic blood samples will be collected for GSK3342830 and potential metabolites. At the end of the study the saved blood samples from a predicted therapeutically-relevant dose level and higher dose level for plasma PK analysis of parent and the highest dose level completed for metabolite profile, will be transferred to a GSK specified laboratory. Details of PK sample collection and storage will be provided in the Study Reference Manual.
5. Pooled urine samples will be collected over the following time intervals: pre-dose (within a 24-hour period before dosing, may begin on Day -1) and 0 to 4, 4 to 8, 8 to 12, 12 to 24, and 24 to 48 hours post-dose. Two aliquots of urine samples for baseline analysis may be collected from any time after admission to just before dosing on Day 1. At the end of the study, the saved urine samples from a predicted therapeutically-relevant dose level and higher dose level for urinary PK analysis of parent and the highest dose level completed for potential metabolite profile, will be transferred to a GSK specified laboratory. Urine will be collected in opaque bottles to maintain blind of blinded study site personnel. Details of urine sample collection and storage will be provided in the Study Reference Manual.
6. Continuous dual-lead telemetry will be initiated on Day -1 at least 8 hours before treatment administration on Day 1 and will continue until 48 hours post dose.
7. Subjects will be discharged from the clinical unit after the 48-hour post-dose assessments are complete.

Table 5 Time and Events Table: Part 2 - Repeat Dose Escalation

Procedure	Study Day															
	1	2	3	4	5	6	7	8	9	10	11	12	13	14	15	16
Randomization	X															
12-lead ECG ¹	X	X	X	X	X	X	X	X	X	X	X	X	X	X	X	X
Vital signs (BP, HR, oral temperature, respiration rate) ²	X	X	X	X	X	X	X	X	X	X	X	X	X	X	X	X
Fasting clinical chemistry, hematology, and urinalysis tests ³		X			X					X					X	
Treatment administration ⁴	X	X	X	X	X	X	X	X	X	X	X	X	X	X	X	X
Blood collection for pharmacokinetics ⁵	X		X			X			X			X	X		X	
Urine collection for pharmacokinetics ⁶	X	X													X	X
Continuous cardiac monitoring ⁷	X←Continuous review→															
AE review	X←-----Continuous review----->															
SAE review	X←-----Continuous review----->															
Concomitant medication review	X←-----Continuous review----->															
Discharge from inpatient unit ⁸																X

AE = adverse event, BP = blood pressure, ECG = electrocardiogram, HR = heart rate, SAE = serious adverse event.

NOTES:

1. Triplicate 12-lead ECGs will be obtained at least 5 minutes apart within 1 hour before the start of infusion (pre-dose) on Day 1. Single ECGs will be obtained at 0.5, 1, 1.5, 2, 3, 4, 6, and 12 hours after the start of infusion on Day 1 and Day 15, within 1 hour before the start of the morning infusion on Days 2, 3, 4, 5, 6, 7, 8, 9, 10, 11, 12, 13, and 14, and in the morning on Day 16.
2. Vital signs will be measured within 1 hour before the start of infusion (pre-dose) and at 0.5, 1, 1.5, 2, 3, 4, 6, and 12 hours after the start of infusion on Days 1 and 15, within 1 hour before the start of the morning infusion and on Days 2, 3, 4, 5, 6, 7, 8, 9, 10, 11, 12, 13, and 14, and in the morning on Day 16.
3. An aliquot of the urine sample will be collected for neutrophil gelatinase-associated lipocalin (NGAL) and kidney injury molecule 1 (KIM-1). These samples may be analyzed after the end of the study if a clinical signal is detected. Instructions for collection and storage of these urine samples are included in the Study Reference Manual. Hematology assessments on Days 5 and 15 will also include total iron, total iron binding capacity, ferritin, haptoglobin, ceruloplasmin and reticulocytes. The albumin to creatinine ratio will be determined using the first morning void urine on Days 5 and 15. Urinalysis assessments before dosing on Day 15 will also include urine color.
4. GSK3342830 or placebo will be administered as a single IV infusion in the morning on Day 1, TID IV infusions (approximately every 8 hours) on Days 2, 3, 4, 5, 6, 7, 8, 9, 10, 11, 12, 13, and 14, and as a single IV infusion in the morning on Day 15. The planned infusion duration time is 1 hour.
5. Pharmacokinetic samples for GSK3342830 and potential metabolites will be collected on Day 1 at the following time points: pre-dose (within 15 minutes before dosing) and 0.5, 1 (end of infusion), 1.25, 1.5, 2, 2.5, 3, 3.5, 4, 4.5, 5, 6, 8, 10, 12, 16, and 24 hours after the start of infusion. Single pre-dose trough samples will be taken on the mornings of Days 3, 6, 9, 12, and 13. Serial samples will be collected on Day 15 at the following time points: pre-dose (within 15 minutes before dosing) and 0.5, 1 (end of infusion), 1.25, 1.5, 2, 2.5, 3, 3.5, 4, 4.5, 5, 6, and 8 hours after the start of infusion. At the end of the study, the saved blood samples from a predicted therapeutically-relevant dose level and higher dose level for plasma PK analysis of parent and from the highest dose level completed for potential metabolite profile will be transferred to a GSK specified laboratory. Details of PK sample

collection and storage will be provided in the Study Reference Manual.

6. Pooled urine samples will be collected on Day 1 and Day 15 over the following time intervals: pre-dose (within a 24-hour period before dosing, may begin on Day -1) and 0 to 8 and 8 to 24 hours post-dose. Two aliquots of urine samples for baseline analysis may be collected from any time after admission to just before dosing on Day 1. At the end of the study, the saved urine samples from a predicted therapeutically-relevant dose level and higher dose level for urinary PK analysis of parent and from the highest dose level completed for potential metabolite profile, will be transferred to a GSK specified laboratory. Urine will be collected in opaque bottles to maintain blind of blinded study site personnel. Details of urine sample collection and storage will be provided in the Study Reference Manual.
7. Continuous dual-lead telemetry will be initiated on Day -1 at least 8 hours before treatment administration on Day 1 and will continue until 48 hours post dose.
8. Subjects will be discharged from the clinical unit after the Day 16 assessments are complete.

Table 6 Time and Events Table: Follow-up Visit; Single and Repeat Dose Escalation (Part 1 and Part 2) and Single Dose (Part 3)

Procedure	Follow-up Visit (7 to 10 days post last dose or early termination)
Adverse event/serious adverse event review	X
Concomitant medication review	X
Brief physical examination	X
12-lead electrocardiogram	X
Vital signs	X
Urine β -human chorionic gonadotropin pregnancy test (women of child-bearing age)	X
Clinical chemistry, hematology, and urinalysis tests ¹	X

NOTE:
 
1. An aliquot of the urine sample will be collected for neutrophil gelatinase-associated lipocalin (NGAL) and kidney injury molecule 1 (KIM-1). These samples may be analyzed after the end of the study if a clinical signal is detected. Instructions for collection and storage of these urine samples are included in the Study Reference Manual. Hematology assessments will also include total iron, total iron binding capacity, ferritin, haptoglobin, ceruloplasmin and reticulocytes. The albumin to creatinine ratio will be determined using the first morning void urine as described in Section 7.3.7.
	

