Based on the results of preclinical studies of GSK3342830 as well as clinical adverse events (AEs) previously associated with cephalosporin antibiotics and antibiotics in general, the following areas of interest have been identified for safety monitoring in the early clinical development program for GSK3342830: potential effects on heart rate, blood pressure, and body temperature; potential effects on the respiratory cycle; injection

site reactions, potential effects on kidney function, chromaturia and colored stool, and hematologic findings; and potential interactions with 5-hydroxytryptamine, serotonin (5-HT)-3 receptors. All of these effects showed evidence of reversibility after a 1-month recovery period and were considered non-adverse, except for the injection site reactions, which were considered adverse. In 4-week Good Laboratory Practice (GLP) studies, local irritation and inflammation occurred at the two higher doses (1000 and 2000 mg/kg/day) tested and irritation occurred at the 50 and 100 mg/mL doses in rat and monkey, respectively. It is uncertain whether these local effects were due to the GSK3342830 itself or to the high osmolalities (≥ 740 mOsm) of the dosing formulations, or both. The results of these studies suggest that limiting the concentrations to no greater than 25 mg/mL is expected to reduce or eliminate the irritation potential in clinical formulations.

The findings for GSK3342830 in the toxicology and safety pharmacology studies support the proposed clinical trial. The only adverse findings were irritation and injury at the injection sites that were believed to be due to the high concentrations (50 - 200 mg/mL) and/or osmolalities (740 - 2164 mOsm) of the formulations (Stranz, 2002). Use of lower concentrations should avoid this issue in the clinic. The other findings in the 4-week GLP studies were non-adverse, secondary to the local irritation, or were of slight severity. Hemodynamic findings in monkey and respiratory findings in rat were relatively slight, have acceptable safety margins at clinically predicted doses and, if required, are able to be monitored.

Refer to GSK3342830 Investigator's Brochure (IB) [GSK Document Number [2015N255155_00](#)] for complete information regarding GSK3342830.

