Renal findings	
 • Kidney: hyaline droplets in proximal tubules, weight increase in both species 
 • Hyaline droplets associates with absorption and secretion of the cephem antibiotics in lysosome • No degenerative changes • Probably mixture of drug and protein (stimulation of lysosomal turnover) • Accompanied by increases in urinary N-acetyl-β-D-glucosaminidase (exploratory biomarker of lysosomal enzyme) at all doses and slight change in urinary albumin at 2000 mg/kg (relevance unclear) 	
 • Inclusion/Exclusion 
 • Healthy subjects • Serum creatinine greater than the upper limit of normal (ULN) • Estimated glomerular filtration rate (eGFR) <90 mL/min/1.73 m² as calculated by the Chronic Kidney Disease Epidemiology Collaboration formula • Albumin to creatinine ratio (ACR) ≥0.03 mg/mg • Urinalysis negative for blood/protein • Monitor: 
 • Serum blood urea nitrogen, creatinine, eGFR, electrolytes, urinalysis • ACR during the study • Criteria to pause Part 1 progression or interrupt Part 2 dosing 
 • Creatinine change >0.3 mg/dL without alternative cause • New blood in urinalysis confirmed by microscopy without alternative cause • ACR ≥0.03 mg/mg
Injection site reactions	
 • Local irritation 
 • Gross: discoloration, hardening, wound, thrombosis • Histology: ulcer, perivascular/vascular inflammation, thrombus (1000/2000 mg/kg/day; rats and monkeys) • Considered due to high osmolality of the dosing formulations 	
 • Reduced osmolality preparation • Monitor injection site including proximal limb for vascular change

Potential Risk of Clinical Significance	Summary of Data/Rationale for Risk	Mitigation Strategy

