5.4. Withdrawal/Stopping Criteria

The following actions must be taken in relation to a subject who fails to attend the clinical unit for a required study visit:

- The site must attempt to contact the subject and re-schedule the missed visit as soon as possible.
- The site must counsel the subject on the importance of maintaining the assigned visit schedule and ascertain whether or not the subject wishes to and/or should continue in the study.
- In cases where the subject is deemed ‘lost to follow up’, the investigator or designee must make every effort to regain contact with the subject (where possible, 3 telephone calls and if necessary a certified letter to the subject’s last known mailing address or local equivalent methods). These contact attempts should be documented in the subject’s medical record.
- Should the subject continue to be unreachable, only then will he/she be considered to have withdrawn from the study with a primary reason of “lost to follow up”.

A subject may withdraw from study treatment at any time at his/her own request, or may be withdrawn at any time at the discretion of the investigator for safety, behavioral, or administrative reasons. If a subject withdraws from the study, he/she may request destruction of any samples taken, and the investigator must document this in the site study records.

This protocol defines several clinical laboratory values, 12-lead ECG values, vital sign values, and additional safety criteria that, if observed and confirmed, mandate cessation of drug dosing and further evaluations. Any laboratory result that meets the stopping criteria should be repeated once to confirm the value before the subject is withdrawn from the study.

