5.4.3. Renal Stopping Criteria

Study treatment will be discontinued for a subject who meets any of the following criteria:

- Persistent (confirmed on recheck) elevation of serum creatinine (>0.3 mg/dL) without an alternative cause identified
- Albumin to creatinine ratio ≥ 0.03 mg/mg
- New blood in urinalysis confirmed by microscopy without an alternative cause identified

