Other Screening Tests	
 • Human immunodeficiency virus • Hepatitis B surface antigen • Hepatitis C antibody • Follicle-stimulating hormone and estradiol (as appropriate) • Alcohol, cotinine, and drug screen (to include at minimum: amphetamines, barbiturates, cocaine, opiates, cannabinoids and benzodiazepines) • β-human chorionic gonadotropin pregnancy test (if female of child-bearing age; serum at screening and urine at Day -1 and follow-up) 			

ACR = albumin to creatinine ratio, ALT = alanine aminotransferase, AST = aspartate aminotransferase, KIM-1 = kidney injury molecule 1, MCH = mean corpuscular hemoglobin, MCHC = mean corpuscular hemoglobin concentration, MCV = mean corpuscular volume, NGAL = Neutrophil gelatinase-associated lipocalin, RBC = red blood cell, TIBC = total iron binding capacity, WBC = white blood cell
 
Footnotes are on the next page.
				

NOTES:

1. In Parts 1 and 3, analyzed on Day –1 and at Follow-up visit. In Part 2, analyzed on Day –1, Day 5, Day 15, and at Follow-up visit.
2. Blood samples will be collected on Day –1, predose (at least 1 hour before dosing) on Days 5, and 15, and at Follow-up visit..
3. Details of Liver Chemistry Stopping Criteria and Required Actions and Follow-Up Assessments after liver stopping or monitoring event are given in Section 5.4.1, Appendix 2, and Appendix 3.
4. The ACR on urine albumin and creatinine will be determined using the first morning void urine at Screening and Follow-up visit for all subjects in both parts of the study. In addition, the ACR will be determined on Day 2 in Parts 1 and 3, and Days 5 and 15 in Part 2. Screening ACR may be performed on urine during the screening visit. Subjects should be provided a sterile urine transport container and instructions on how to collect a first void urine at home for screening. In the event a subject fails by ACR, the subject should be contacted to bring back first void urine for recheck. For the Follow-up visit, subjects must be provided a sterile urine transport container on discharge from the clinical unit and instructed to bring back the first morning void urine on the day of their return Follow-up visit.
5. An aliquot of the remaining urine samples will be banked and may be analyzed for NGAL and KIM-1 after the end of the study if a clinical signal is detected. Instructions for collection and storage of these urine samples are included in the Study Reference Manual.

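### In Part 2 the mandatory albumin-to-creatinine stopping rule is checked on treatment only on Days 5 and 15, with 30 of 41 infusions between the samples; a Day 10 test would halve that gap

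*Protocol*

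**What the plan says.** Protocol Section 5.4.3 lists three renal criteria, any one of which requires study treatment to be discontinued. One is "Albumin to creatinine ratio ≥ 0.03 mg/mg". Unlike the creatinine and blood-in-urine criteria beside it, it has no exception for an alternative cause. The renal row of Section 4.6.1 includes the same threshold under "Criteria to pause Part 1 progression or interrupt Part 2 dosing". Section 5.4 adds that a laboratory result meeting a stopping criterion "should be repeated once to confirm the value before the subject is withdrawn from the study".

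The on-treatment schedule is stated twice in the protocol and is consistent. Table 5 note 3 (Section 7.1) reads "The albumin to creatinine ratio will be determined using the first morning void urine on Days 5 and 15", and Table 7 note 4 (Section 7.3.7) reads "In addition, the ACR will be determined on Day 2 in Parts 1 and 3, and Days 5 and 15 in Part 2". The only other ACR measurements in Part 2 are at Screening and Follow-up. The SAP repeats the Days 5 and 15 schedule in Appendix 1, Part 2 table, note 3.

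Table 5 schedules clinical chemistry, hematology and urinalysis on Days 2, 5, 10 and 15. Day 10 is therefore already a urinalysis day, but without ACR.

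**The concern.** A within-subject stopping rule protects the subject only if it is checked while there is still dosing to stop. By the Day 15 void, all but one infusion has been given. Albuminuria that starts after Day 5, without a rise in creatinine or blood in the urine, would not meet its mandatory rule until treatment was essentially over.

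The protocol itself treats the kidney as an area of interest (Section 2.2), and Section 4.6.1 reports a "slight change in urinary albumin at 2000 mg/kg (relevance unclear") in animals. Part 2 is meant to establish tolerability over 14 days of dosing (Section 4.4). This rule goes unchecked between the Day 5 and Day 15 voids, which span ten days of three-times-daily dosing.

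**Working it through.** **Inputs**
- Dosing: one infusion on Day 1, three per day on Days 2 to 14, one on Day 15 (Section 4.1; Table 5 note 4). The Table 5 treatment row, as extracted, also shows a mark under Day 16; the count follows the text, which ends dosing on Day 15.
- ACR days on treatment: 5 and 15 (Table 5 note 3; Table 7 note 4).
- Part 2 size: about 30 subjects (Section 4.3).
- Assumption: the first morning void comes before that morning's infusion.

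**Step 1: the plan's own figure.** Section 4.1 states 13 days of multiple dosing. Days 2 to 14 give 14 − 2 + 1 = 13, which agrees. The protocol gives no total number of infusions; it is 1 + 13 × 3 + 1 = 41.

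**Step 2: infusions relative to the ACR samples**

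| Interval | Current schedule | With Day 10 added |
|---|---|---|
| Before the Day 5 void | 1 + 3 × 3 = 10 | 10 |
| Day 5 void to Day 10 void | – | 5 × 3 = 15 |
| Day 10 void to Day 15 void | – | 5 × 3 = 15 |
| Day 5 void to Day 15 void | 10 × 3 = 30 | – |
| After the Day 15 void | 1 | 1 |
| Total | 41 | 41 |

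The current gap is 30/41 = 73% of infusions. The longest gap falls from 30 infusions to 15.

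**Step 3: sensitivity to void timing.** If the Day 5 void came after the morning infusion and the Day 15 void before it, the gap would be 29. With the order reversed it would be 31.

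**Step 4: infusions a positive result could spare.** Assume the Section 5.4 repeat is also a first morning void, taken one or two days later. Assume too that its result is back that morning and that dosing continues meanwhile. The repeat then costs 3 or 6 infusions.
- Day 5 positive: 31 remain; 31 − 3 = 28 or 31 − 6 = 25 spared.
- Day 10 positive (proposed): 15 + 1 = 16 remain; 16 − 3 = 13 or 16 − 6 = 10 spared.
- Day 15 positive: 1 remains. None is spared if dosing continues until the repeat; one is spared if the last infusion is withheld.

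Each further infusion given while the repeat result is awaited takes one off these figures.

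**Step 5: cost in transient positives.** The documents give no rate. Assuming a 1% to 5% chance per sample, one extra sample in 30 subjects gives 30 × 0.01 = 0.3 to 30 × 0.05 = 1.5 initial positives needing a repeat.

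**The case against.** The strongest reply is that this is a preference about sampling frequency, not an error. The schedule is the same everywhere it appears, nothing in the documents promises denser ACR sampling, and every laboratory rule is blind between samples. That is correct.

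Second, renal safety is still watched in the gap. On Day 10, serum creatinine and blood in urine are tested, and both are Section 5.4.3 criteria. Dipstick protein is run as well, with microscopy if blood or protein is abnormal, and clinically significant abnormal values are repeated until normal or back to baseline (Section 7.3.7). This stands as partial cover, but dipstick protein is not a Section 5.4.3 criterion. It leads to action through a Grade 3 urinalysis finding, where discontinuation is only to be considered (Section 5.4.7), or through investigator judgement (Section 5.4.6). The Day 10 NGAL and KIM-1 aliquots may be analyzed only after the study ends.

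Third, Sections 4.1, 7 and 7.3 allow assessments to be added on emerging or newly available data. Part 1 contributes a Day 2 ACR from each single-dose cohort before Part 2 begins. The Day 5 and Day 15 results of each Part 2 cohort can inform the next escalation (Section 4.2). These routes are real but reactive: they protect later subjects and do not plan a mid-course check for those already dosing.

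Fourth, the expected harm is small. The renal row of Section 4.6.1 records "No degenerative changes". Of the effects listed as areas of interest, kidney function among them, Section 2.2 says "All of these effects showed evidence of reversibility after a 1-month recovery period and were considered non-adverse", with injection site reactions the stated exception. This is accepted and sets the severity.

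**Conclusion.** The point holds as a cheap improvement of low severity. The protocol makes an ACR threshold mandatory for discontinuation, yet measures it so that 30 of 41 infusions (29 to 31, depending on void timing) pass between the two on-treatment samples. Only Day 5 leaves meaningful dosing to stop.

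The gain from Day 10 is conditional. It applies to albuminuria that is present by Day 10 and was not detectable on Day 5. There, a confirmed positive spares about 10 to 13 infusions, on the Step 4 assumptions about repeat timing, a same-day result and continued dosing. Onset after Day 10 would still be found only on Day 15, as now.

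Four stronger readings are not supported:
- *Renal safety is unmonitored for ten days.* The Day 10 chemistry and urinalysis rule this out; only the ACR rule is unchecked.
- *A Day 10 positive would spare all 16 remaining infusions.* That leaves no time for the repeat. If the repeat is a first morning void, it cannot be taken before Day 11, after three more infusions if dosing continues.
- *The toxicity grades show how much albuminuria a dipstick would miss.* Appendix 6 grades the severity of proteinuria. It does not give dipstick sensitivity, and it concerns protein rather than albumin.
- *Renal injury is to be expected.* The animal albumin change was slight, of unclear relevance, and reported without naming the species.

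**What to change.** Add Day 10 to the Part 2 ACR days in Protocol Table 5 note 3 and Table 7 note 4, and in SAP Appendix 1, Part 2 table, note 3. Use the first morning void, alongside the urinalysis already scheduled that day. Leave the 0.03 mg/mg threshold and the Section 5.4 repeat rule unchanged. Make the change by protocol amendment, since the Note to File route in Section 7 is tied to newly available data.

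The cost is one extra urine assay per subject, about 30 in all. Subjects are already confined to the unit, so there is no added visit or blood draw. The occasional transient positive is handled by the existing repeat rule.
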